9.4.3.3 Clinical benefit rate

The CBR will be defined as the proportion of participants with clinical benefit (confirmed CR or PR as BOR, or SD lasting at least 6 months). Specifically, participants will be considered as clinical benefit responders if they achieve a CR or PR as BOR, or have an overall response recorded as SD at 6 months (ie, 26 weeks) or later from first IMP intake, allowing for the ± 7 days visit window for tumor assessment scheduled at 27 weeks.

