3 OBJECTIVES AND ENDPOINTS

Table 1 - Objectives and endpoints

Objectives	Endpoints
Primary	
• To determine the antitumor activity of SAR444245 in combination with other anticancer therapies• Objective response rate (ORR) defined as the proportion of participants who have a confirmed complete response (CR) or partial response (PR) determined by Investigator per Response Evaluation Criteria in Solid Tumors (RECIST) 1.1 (1)
Secondary	
• To assess the safety of SAR444245 in combination with other anticancer therapies• To assess other indicators of antitumor activity• Incidence of treatment emergent adverse events (TEAEs), serious adverse events (SAEs), laboratory abnormalities according to National Cancer Institute Common Terminology Criteria for Adverse Events (NCI CTCAE) V5.0 and American Society for Transplantation and Cellular Therapy (ASTCT) consensus grading (2)• Time to response (TTR), defined as the time from the first administration of investigational medicinal product (IMP) to the first tumor assessment at which the overall response was recorded as PR or CR that is subsequently confirmed and determined by Investigator per RECIST 1.1• Duration of response (DoR), defined as the time from first tumor assessment at which the overall response was recorded as CR or PR that is subsequently confirmed until documented progressive disease (PD) determined by Investigator per RECIST 1.1 or death from any cause, whichever occurs first• Clinical benefit rate (CBR) including confirmed CR or PR at any time or stable disease (SD) of at least 6 months determined by Investigator per RECIST 1.1.• Progression-free survival (PFS), defined as the time from the date of first IMP administration to the date of the first documented disease progression determined by Investigator as per RECIST 1.1 or death due to any cause, whichever occurs first• Plasma concentrations and where applicable PK parameters of SAR444245• Incidence of anti-drug antibodies (ADAs) against SAR444245
Exploratory	

For China, please see [Section 10.7](#) for details.

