9.4.2 Primary endpoint(s)

9.4.2.1 Objective response rate

For all cohorts, the ORR is defined as the proportion of participants who have a confirmed CR or PR as per Investigator's assessment.

The BOR is the best overall response observed from the date of first IMP until disease progression, death, cut-off date or initiation of post-treatment anti-cancer therapy, whichever occurs first.

ORR and BOR will be summarized with descriptive statistics. In addition, two-sided 90% CIs will be computed using the Clopper-Pearson method. All objective responses need to be confirmed by a subsequent assessment performed at least 4 weeks apart from the initial response observation.

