6 STUDY INTERVENTION(S) AND CONCOMITANT THERAPY

6.1 STUDY INTERVENTION(S) ADMINISTERED

Please refer to the master protocol.

For study treatment duration, completion of Cycle 35 is applicable for Cohort A.

Dosing sequence: [REDACTED]

In addition, if a participant has immune unconfirmed progression of disease (iUPD) and is clinically stable, it is at the discretion of the Investigator to continue treating the participant with the assigned treatment per protocol until progression of disease is confirmed (iCPD) at least 4 weeks, but no longer than 8 weeks from the date of the scan suggesting progression of disease (Section 10.9).

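### The working rule for the stable-disease route of the clinical benefit rate does not match the definition it is meant to specify

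*Protocol*

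**What the plan says.** Table 1 (master protocol section 3) lists the endpoint as "Clinical benefit rate (CBR) including confirmed CR or PR at any time or stable disease (SD) of at least 6 months". The first sentence of section 9.4.3.3 agrees: "confirmed CR or PR as BOR, or SD lasting at least 6 months".

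The next sentence turns this into a rule with two routes:
- Response route: "participants will be considered as clinical benefit responders if they achieve a CR or PR as BOR".
- SD route: participants who "have an overall response recorded as SD at 6 months (ie, 26 weeks) or later from first IMP intake". The week-27 scan is given a tolerance of one week either side.

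The SD route rests on the label of a single visit. It does not mention a visit read as unconfirmed CR or PR, and it sets no condition about earlier progression or new treatment. By contrast, section 9.4.2.1 counts BOR only "until disease progression, death, cut-off date or initiation of post-treatment anti-cancer therapy, whichever occurs first". DoR (9.4.3.2) and PFS (9.4.3.4) end at the first documented PD or at death and have rules for new anticancer therapy. Substudy 01 section 10.9.1 measures the length of SD from treatment start to progression.

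**The concern.** The definition is about a duration, and the working rule is about a label. They agree for most participants but not for all. A participant can be free of progression well past six months and fail the rule because the tumor shrank too much at week 27 to be called SD. Another can have a PFS event before week 26 and pass the rule because a later scan is read as SD.

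CBR could then contradict BOR, SD duration or PFS for the same person. The SD route also matters in this trial. Substudy 01 section 9.5 takes an ORR of 5% as the minimum meaningful effect, which is 2 of 40. If confirmed response is near that level, CBR will consist largely of participants who enter by the SD route. Assessment is open-label and by the Investigator, so edge cases are better settled before the data are seen.

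**Working it through.** **The plan's own figure.** The week-27 scan with its 7-day window opens at 27 × 7 − 7 = 182 days, and 26 × 7 = 182 days. The 26-week cut therefore matches the scan schedule and is not in question.

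**Inputs.** Scans every 9 weeks to week 45, so weeks 9, 18, 27 and 36 (section 8.1.1). Responses confirmed at least 4 weeks later (9.4.2.1). Cohort size 40 (Substudy 01 section 9.2). 90% intervals (9.4.1).

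**Excluded participant.** Take SD at week 9, SD at week 18, PR at week 27, PD at week 36.
- The PR is unconfirmed, so BOR is SD (9.4.2.1; Appendix 8 requires confirmation for PR and one SD reading for SD).
- SD duration by Substudy 01 section 10.9.1 and PFS by 9.4.3.4 are both 36 weeks, about 8.3 months.
- First sentence of 9.4.3.3: clinical benefit, yes.
- Working rule: no scan at week 26 or later is labelled SD, so no.
- With SD instead of PR at week 27, that is, less shrinkage, the participant would count.

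**Counted participant.** Take SD at week 9, PD at week 18, SD at week 27.
- Section 8.1.1 allows confirmatory imaging after a first PD if the participant is clinically stable. For unconfirmed progression, Substudy 01 section 6.1 says "it is at the discretion of the Investigator to continue treating the participant with the assigned treatment per protocol" until PD is confirmed, 4 to 8 weeks after the suspicious scan (here weeks 22 to 26).
- PFS event at week 18. First sentence of 9.4.3.3: no. Working rule: SD label at week 27, so yes.

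**How many patterns.** All sequences of SD, PR and PD of one to four scans over these weeks were listed. The literal rule was compared with this one: confirmed PR before PD, or any non-PD scan at 26 weeks or later with no earlier PD. A PR was taken as confirmed if the next listed scan was also PR.

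| Imaging | Sequences | Wrongly excluded | Wrongly counted |
|---|---|---|---|
| Stops at first PD | 3+6+12+24 = 45 | 4 | 0 |
| Continues after PD | 3+9+27+81 = 120 | 4 | 33 |

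The four excluded are SD-SD-PR, PR-SD-PR, SD-SD-PR-PD and PR-SD-PR-PD. If PR-SD-PR were accepted as a confirmed response, two would remain. These are counts of possible patterns, not frequencies.

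**Still counted.** PR at week 9 or 18 then SD at week 27; PR at week 27 then SD at week 36; PR at weeks 27 and 36, which is a confirmed response.

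**Missing word.** The response route omits confirmed. Taken alone, it would admit PR at week 9 followed by PD at week 18. The sentence before it and 9.4.2.1 require confirmation.

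**Size.** 1/40 = 2.5 percentage points per participant. With Clopper-Pearson limits (stated for ORR, assumed here for CBR): 10/40 = 25.0% (14.2–38.7), matching Table 9 of Substudy 01; 11/40 = 27.5% (16.3–41.4).

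**The case against.** The strongest reply is that the second sentence only clarifies the first and must be read with it. SD that ended in PD at week 18 did not last six months, and Substudy 01 section 10.9.1 says as much. Imaging normally stops at PD, and then no pattern is wrongly counted. Substudy 01 allows only a short window to confirm PD, so the second error needs a first PD that is not confirmed and then reverses. A PD through a new lesion stays PD while the lesion persists. Scans are not required once another therapy has started, so the missing stop at new therapy will rarely matter. Some excluded patterns may be resolved by a later scan before the final cut-off. The SAP, not at hand, may settle the derivation.

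Most of this stands, and it limits the point. It does not remove it. The protocol did not leave the derivation open: it wrote a rule, and a programmer following that rule gets a different answer from the definition. The exclusion error occurs even when imaging stops at PD.

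A reader might infer more than the text supports:
- That everyone needs an SD scan at week 26 or later. Not so: CR or PR as BOR qualifies without one.
- That unconfirmed PRs are dropped in general. Only those without an SD label from week 26 on are.
- That CBR will be inflated by progressed participants, or no longer measures its objective. The documents give no frequency, and the two errors act in opposite directions.

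**Conclusion.** The point holds as a mismatch between a definition and its working rule, worth correcting but limited in effect. Taken literally, the SD route excludes some participants who are progression-free beyond 26 weeks and, where scans continue after a first PD, can count some who have progressed. The omitted confirmation in the response route is a further wording slip.

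Each misclassified participant moves CBR by 2.5 points in a cohort of 40, or slightly more if the efficacy population is smaller. The number affected and the direction of any net error cannot be derived from the documents. CBR is a descriptive secondary endpoint with no hypothesis test, and the futility rule uses ORR, so no trial decision written in the protocol depends on it. The conclusion assumes that the second sentence of 9.4.3.3 will be programmed as written and that the SAP does not override it.

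**What to change.** Replace the second sentence of 9.4.3.3, and use the same text in the SAP, with a rule of this content: a participant has clinical benefit with a confirmed CR or PR as BOR, or with an overall response of SD or better (unconfirmed CR or PR included) at an assessment on day 182 or later from first IMP, provided that no RECIST 1.1 PD was documented and no new anticancer therapy was started before that assessment.

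This concerns the derivation only. It needs no new data and no change to imaging or treatment. Substudy 01 section 9.4.3 refers back to the master protocol, so one edit carries through there. The cost is one sentence, best settled before the first cohort is analysed.

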9.4.3.4 Progression-free survival (RECIST 1.1)

Progression-free survival is defined as the time from the date of first IMP to the date of the first documentation of objective progressive disease or death due to any cause, whichever occurs first.

The analysis of PFS will be based on the following censoring rules:

- If progression or death is not observed before the cut-off date and prior to the initiation of a further anticancer therapy, then PFS will be censored at the date of the last valid tumor assessment performed before the cut-off date or date of initiation of a further anticancer therapy, whichever is earlier.
- A participant without event (death or disease progression) and without any valid post-baseline tumor assessment will be censored at the day of first IMP (Day 1).

Progression-free survival will be summarized using Kaplan-Meier methods. The median PFS times and associated 90% CI will be provided.

9.4.3.5 Adverse events

All AEs will be categorized according to NCI-CTCAE v5.0 (except for CRS and ICANS that will be graded using ASTCT criteria) and classified by system organ class (SOC) and Preferred Term (PT) according to the latest available version of the Medical Dictionary for Regulatory Activities (MedDRA).

- Pre-treatment AEs are defined as any AEs occurring during the pre-treatment period.
- Treatment-emergent AEs are defined as AEs that develop, worsen (according to the Investigator's opinion), or become serious during the treatment-emergent period.
- Post-treatment AEs are defined as AEs that are reported during the post-treatment period.

For participants with multiple occurrences of the same PT, the maximum grade will be used.

The primary focus of AE reporting will be on TEAEs. Pre-treatment and post-treatment AEs will be described separately.

Treatment-emergent adverse events:

An overall summary of TEAEs will be provided. The number and percentage of participants experiencing any of the following will be provided:

- TEAEs
- Grade ≥ 3 TEAEs
- Grade 5 TEAEs (any TEAE with a fatal outcome during the treatment-emergent period)
- Serious TEAEs
- Serious treatment-related TEAEs
- TEAEs leading to permanent partial intervention discontinuation (any of the IMP components)
- TEAEs leading to permanent full intervention discontinuation
- Treatment-related TEAEs
- Treatment-related TEAEs Grade ≥ 3

Number and percentage of participants experiencing TEAEs by primary SOC and PT will be summarized by NCI-CTCAE v 5.0 or ASTCT grade (all grades and Grade ≥ 3). Missing grades, if any, will be included in the "all grades" category. Similar summaries will be prepared for treatment-related TEAEs, TEAEs leading to permanent discontinuation of SAR444245, or permanent discontinuation of other anticancer therapies in combination, TEAEs leading to full intervention discontinuation, TEAEs leading to dose modification, serious TEAEs, TEAEs with fatal outcome, AESIs, and AEs/SAEs occurring during the post-treatment period. In addition, the number (%) of participants with any Grade 5 AE (TEAE and post-treatment) will be summarized.

The following deaths summaries will be generated:

- Number and percentage of participants who died by study period (treatment-emergent period, post-treatment period) and reasons for death (disease progression, AE, or other reason).
- All TEAEs leading to death by primary SOC and PT showing number and percentage (%) of participants.

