 - Number and percentage of participants experiencing treatment-emergent adverse events (TEAEs) by primary System Organ Class (SOC) and Preferred Term (PT) will be summarized by National Cancer Institute Common Terminology Criteria for Adverse Events (NCI-CTCAE) V 5.0 or American Society for Transplantation and Cellular Therapy (ASTCT) grade (all grades and Grade ≥ 3) for the exposed population. Similar summaries will be prepared for treatment-related TEAEs, TEAEs leading to permanent partial intervention discontinuation (any of the IMP components), TEAEs leading to permanent full intervention discontinuation, TEAEs leading to dose modification, serious TEAEs, TEAEs with fatal outcome, adverse events of special interest (AESIs), and AEs/SAEs occurring during the post-treatment period. In addition, the number (%) of participants with any Grade 5 AE (TEAE and post-treatment), participants who died by study period (treatment-emergent period,

[figure not shown]
post-treatment period) and reasons for death will be summarized. Immune Cell-Associated Neurotoxicity Syndrome (ICANS) and cytokine release syndrome (CRS) events will be graded using ASTCT Consensus Grading and will be summarized separately.

- Hematology and clinical chemistry results will be graded according to the NCI-CTCAE V 5.0, when applicable. Number and percentage of participants with laboratory abnormalities (all grades and by grade) using the worst grade during the on-treatment period will be provided for the exposed population.
- **Analysis of other secondary endpoints:**
 - Plasma concentrations of each cohort by SAR444245 will be summarized with descriptive statistics. Where applicable, in addition PK parameters for SAR444245 will be summarized with descriptive statistics

Data Monitoring/Other Committee: Yes (see [Section 10.1.5](#) for details)

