8.3.1 Time period and frequency for collecting AE and SAE information

All AEs, including adverse events of new onset, as well as worsening of baseline signs and symptoms will be collected throughout study period, from the signing of the informed consent form (ICF) until **30 days** following cessation of study treatment.

All SAEs and AESIs will be collected throughout the study period, from the signing of the informed consent form (ICF) until **90 days** following last administration of study treatment.

All SAEs and AESI will be recorded and reported to the Sponsor or designee immediately and under no circumstance should this exceed 24 hours, as indicated in Appendix 3 ([Section 10.3](#)). The Investigator will submit any updated SAE data to the Sponsor within 24 hours of it being available.

Investigators are not obligated to actively seek information on AEs or SAEs after conclusion of the study participation. However, if the Investigator learns of any SAE, including a death, at any time after a participant has been discharged from the study, and he/she considers the event to be reasonably related to the study intervention or study participation, the Investigator must promptly notify the Sponsor.

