9.3 POPULATIONS FOR ANALYSES

The following populations for analyses are defined ([Table 3](#)):

Table 3 - Populations for analyses

Population	Description
Exposed	Exposed population will include all participants who have given their informed consent and received at least one dose (even incomplete) of IMP (SAR444245 or other anticancer therapies).
Efficacy	Efficacy population will include all participants from the exposed population with at least one evaluable post-baseline tumor assessment or who permanently discontinued study treatment.
PK	The PK population will include all participants from the exposed population with at least 1 PK concentration available after the first dose of study intervention.
PDy	The PDy population will include all participants from the exposed population with at least 1 PDy parameter assessed after the first dose of study intervention.

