9.4.1 General considerations

This study is not intended to explicitly test a hypothesis, 90% CIs will be provided for primary and secondary efficacy endpoints for descriptive purposes only.

All efficacy analyses will be performed on the efficacy population and analyzed by cohort and pooled cohorts (if applicable). Objective response rate, as well as all other efficacy variables will be derived using the local radiologist's/Investigator's assessment for all cohorts. Unless otherwise specified, the assessments are based on RECIST 1.1.

All safety analyses will be performed on the exposed population by cohort and overall (if applicable). A baseline value will be defined as the latest value or measurement taken up to the first administration of the IMP.

The analysis period will be divided into 3 segments:

- The pre-treatment period is defined as the time from when the participants give informed consent to the first administration of the IMP.
- The on-treatment period (ie, treatment-emergent period) is defined as the time from the first administration of IMP up to 30 days after the last administration of IMP.
- The post-treatment period is defined as the time from the 31 days after the last administration of IMP.

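### The post-treatment AE table covers event types no longer collected after day 30 and counts participants who have not yet entered that period

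*Protocol*

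**What the plan says.** **Tables planned.** The synopsis of the master protocol describes TEAE tables by SOC and PT with number and percentage, by "grade (all grades and Grade ≥ 3) for the exposed population. Similar summaries will be prepared for treatment-related TEAEs". The list of similar summaries, in the synopsis and again in section 9.4.3.5, ends with "AESIs, and AEs/SAEs occurring during the post-treatment period".

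**Denominator.** Section 9.4.1 sets the rule: "All safety analyses will be performed on the exposed population by cohort and overall (if applicable". Under Table 3 in section 9.3, a participant is exposed who gave consent and "received at least one dose (even incomplete) of IMP (SAR444245 or other anticancer therapies". The table defines no subset of participants who reached the post-treatment period.

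**Periods.** In section 9.4.1 the on-treatment period is "defined as the time from the first administration of IMP up to 30 days after the last administration of IMP". The next one follows directly: "The post-treatment period is defined as the time from the 31 days after the last administration of IMP". No end is given.

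**Collection.** Section 8.3.1 begins "All AEs, including adverse events of new onset, as well as worsening of baseline signs and symptoms will be collected throughout study period" and gives the window as "from the signing of the informed consent form (ICF) until 30 days following cessation of study treatment". SAEs and AESIs are collected to 90 days after the last administration. Beyond study participation nothing is actively sought, but an SAE that the investigator learns of and considers related must still be notified. Section 8.3.1 of Substudy 01 adds irAEs to day 90 for Cohort A.

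**The concern.** The analysis sections and the collection section do not describe the same data. General AE collection ends as the post-treatment period opens, yet the plan calls for an AE table of that period in the format of the TEAE table. A low percentage for a nonserious event there would reflect that nobody was asked to record it, and a reader could take it for absence of toxicity.

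The denominator has a separate problem. A participant still being dosed at cut-off, or within 30 days of the last dose, cannot yet have a post-treatment event but is counted as one without an event.

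Delayed toxicity matters here. Section 6.5.4.4 of Substudy 01 notes that irAEs can appear months after the last pembrolizumab dose and that SAR444245 may increase their incidence and severity.

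**Working it through.** **1. The plan's own figure.** The only AE-incidence calculation at hand is in section 9.2 of Substudy 01: the chance of seeing at least one event among 40 participants. With 1 − (1 − p)^40 and p = 1%, 2%, 5%, I get 33.1%, 55.4% and 87.1%, as stated. It takes all 40 as at risk. No figure is given for post-treatment percentages.

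**2. Numerator: planned collection by event type**

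| Event type | Days 31–90 after last dose | After day 90 |
|---|---|---|
| SAE | collected | only related SAEs that come to the investigator's notice |
| AESI, including nonserious | collected | not actively collected |
| irAE, Cohort A | collected | not actively collected |
| Any other nonserious AE | not collected | not collected |

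Active SAE and AESI collection therefore covers 60 days of an open-ended period. With a month of 30.4375 days, a participant m months past the last dose at cut-off has a post-treatment window of 30.4375m − 30 days. The covered share is min(60, window)/window:

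- m = 3: 98%
- m = 6: 60/152.6 = 39%
- m = 12: 60/335.3 = 18%
- m = 18: 60/517.9 = 12%

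These shares show how far the table's label outruns the data. They do not scale a participant percentage.

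**3. Denominator: can participants still be on treatment at the final cut-off?** Yes. In Cohort A treatment may run 35 cycles: 35 × 21 / 30.4375 = 24.1 months. The final cut-off is 18 months after the cohort's LPI.

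**4. Size.** Printed percentage = percentage among those who entered the period × share s of exposed participants who entered it. The documents do not give s, so I assume:

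- exponential time on treatment, median 6 months (λ = ln 2/6 = 0.1155 per month);
- uniform accrual over 12 months, so follow-up at the final cut-off is 18 to 30 months;
- 5% or 15% dying within 30 days of the last dose.

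A participant enters the period if time on treatment plus about 1 month is less than follow-up, so time on treatment must be below a value spread uniformly over 17 to 29 months.

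- No cap on treatment: 1 − (e^(−17λ) − e^(−29λ))/(12λ) = 1 − (0.1403 − 0.0351)/1.3863 = 0.924. Times 0.95 or 0.85: s = 0.88 or 0.79.
- Capped at 24.1 months: 1 − (0.1403 − 0.0614)/1.3863 = 0.943. Times 0.95 or 0.85: s = 0.90 or 0.80.

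So s is about 0.79 to 0.90, and a 10% rate among those who entered prints as 7.9% to 9.0%. Without the early deaths, s is 0.92 to 0.94 and 10% prints as 9.2% to 9.4%. With a 3-month median (no cap) the first factor is 0.993, and s is 0.94 or 0.84.

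In a cohort of 40, 4 participants with an event give 4/40 = 10.0%. If 36 of the 40 entered the period, the figure is 4/36 = 11.1%.

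**The case against.** **The denominator is inferred.** No sentence names one for this table. Section 9.4.3.5 says post-treatment AEs are described separately and that TEAEs are the main focus, and section 9.4 leaves technical detail to the SAP. A SAP could restrict the set. But section 9.4.1 states a rule for all safety analyses, and the synopsis attaches the exposed population to the tables being copied. Restricting the set would depart from that rule.

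**The exposed denominator is a legitimate crude incidence, with early death as a competing event.** This stands in part. Much of the 79–90% shortfall comes from the assumed early deaths, and some statisticians would keep those participants in. The argument does not cover participants still on treatment at cut-off, whose post-treatment period lies ahead.

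**Stronger readings that the documents do not support.**

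- A reader might infer that late toxicity is not ascertained at all. SAEs and AESIs are collected to day 90, and under section 8.3.8 the AESIs may be nonserious and include any irAE of Grade ≥3, ICANS, VLS, CRS of Grade ≥2 and arrhythmia of Grade ≥3.
- A reader might infer that uncollected time dilutes the rates. These are participant percentages, not person-time rates; uncollected time leaves the numerator incomplete.
- A reader might size the effect at the 9-month cut-off, where more participants are still on treatment. That cut-off is for ORR. Safety is a secondary objective, and section 4.1 places secondary objectives at 18 months.
- A reader might conclude that cohorts can no longer be compared. The study is non-randomised, tests no hypothesis and plans no between-cohort safety comparison.

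**Conclusion.** The point holds in a limited form and is worth a cheap correction.

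The numerator limb rests on the text alone. Sections 9.4.1, 9.4.3.5 and the synopsis promise an all-AE table for a period in which section 8.3.1 collects only SAEs and AESIs, plus irAEs in Cohort A, and those only to day 90.

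The denominator limb follows from the general rule for safety analyses, and its size is modest. At the 18-month cut-off, 10% prints as about 8–9% under the assumptions above, and as 9.2–9.4% if early deaths are set aside. Every input to that size is assumed, so it shows the order of magnitude only. Severe late immune toxicity is still captured to day 90. I could not see how the later substudies handle irAE collection, because the text at hand ends within the synopsis of Substudy 02.

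**What to change.** In the synopsis and section 9.4.3.5 of the master protocol:

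1. Restrict the post-treatment percentage table to the event types actively collected after day 30: SAEs, AESIs, and irAEs where the substudy collects them.
2. Count events with onset on days 31 to 90 after the last IMP administration, and say so in the title.
3. Use exposed participants who entered the post-treatment period as the denominator, and print that N.
4. List separately any later related SAEs notified under section 8.3.1, so that the day-90 limit does not drop them.

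State the denominator as an exception to the general rule in section 9.4.1. No new data are needed and no participant is managed differently. The cost is a smaller N and slightly higher percentages.
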